5.2 Exclusion Criteria

Carers who are not able to communicate in English or who do not have capacity to provide informed written consent.

6 RECRUITMENT

6.1 Identifying potential participants

Participants will be identified and approached for consent from multiple sources as described below.

6.1.1 Join Dementia Research

The study will recruit participants through the Join Dementia Research (JDR) website. The study is eligible to be included on the NIHR CRN portfolio as the funder (Alzheimer's Society) is an NIHR non-commercial partner. All studies on the NIHR CRN portfolio are eligible for inclusion on the JDR website to recruit participants.

JDR is an on-line self-registration service that enables volunteers with memory problems or dementia, carers of those with memory problems or dementia and healthy volunteers to register their interest in taking part in research, giving their permission for researchers to contact them about relevant studies. The purpose of JDR is to allow such volunteers to be identified by researchers as potentially eligible for their studies. Researchers can then contact volunteers, in line with the volunteers preferred method of contact, to further discuss potential inclusion.

JDR is funded by Department of Health working in partnership with the charities Alzheimer's Society and Alzheimer's Research UK and is Health Research Authority (HRA) endorsed. The on-line service and all associated documentation, methods of contacting volunteers and handling their data, were reviewed by a specially convened HRA committee which included experts in research ethics, data protection and information governance. Further information on JDR is available here:

<http://www.crn.nihr.ac.uk/dementia/about-dementia-research/join-dementia-research/>

The JDR will register the study and enter in the eligibility requirements including being a carer of someone with dementia and being over the age of 18 living within a specific distance of 3 postcodes (one each in London and North and South England; distances and postcodes can be extended during recruitment according to recruitment progress). Once full ethical approval is granted, the study will become live on the JDR website. When live, the research team members who have been registered to access the study (CI and research assistant) will receive a list of potentially eligible carers. Carers who express a specific interest in this study will be flagged on the system and will be a priority for contacting

by the research team with a requirement to contact them within five days of expressing interest. Potentially eligible carers will be contacted to see whether they would like to be involved in the study and if so, will be sent the PIS. After 3 days we will telephone them to ask if they have read the PIS and are happy to be involved. If they are, a time and date will be arranged for the quantitative interview.

We will record the number of matched volunteers. We will also maintain a log of those we invite to participate but who do not agree to be involved. The log will include the carer's gender, age category (18-39; 40-49, 50-59, 60-69, 70-79 and 80+) and relationship to person with dementia (spouse; adult child; other relative; other friend). This information will not identify the carer but will enable the research team to compare responders and non-responders and to calculate a response rate.

6.1.2 NHS services

NHS services will assist with recruitment as and will include those providing memory assessment services/memory clinics, Community Mental Health Teams, Admiral Nurses (attached to NHS services), GP clinics and other dementia support programmes. Administrative staff or clinicians at NHS sites will identify carers potentially eligible for the study from databases they have routine access to. The research team will not have any access to the service's databases. These databases will only be accessed by clinicians/administrators who have routine access to these databases through their usual employment. Recruiting services will mail by post or email an expression of interest letter (See Appendix 4) to carers. The letter provides brief information about what the study is examining and what participating in the study involves. GP clinics will display flyers promoting the study (Appendix 5). Carers who are interested in learning more about the study can either telephone or email the research team directly using contact details in the letter, or will be able to return a reply slip with a pre-paid envelope with their name and phone number for the research team to call them back. If agreed by the NHS service, a staff member from the service will invite (face-to-face or by telephone) carers to participate. If the carer is interested the NHS staff member will ask them if they agree for their contact details to be forwarded to the researcher or if they would prefer to contact the researcher directly.

NHS services will record a log of people who are sent the expression of interest letter. The log will record the same un-identifiable data as reported above in Section 6.1.1 (gender, age category and relationship).

The following NHS services have agreed to support recruitment:

- Barnet, Enfield & Haringey Mental Health NHS Trust
- Camden and Islington NHS Foundation Trust

The Dementia Research Review Board of the Sussex Partnership NHS Foundation Trust will review the research study at their next board meeting on the 12/10/2017 before they will confirm provisional support for the study.

6.1.3 Non-NHS services

Other non-NHS services including care homes, Admiral nursing services that are not attached to NHS services and branches of the Alzheimer's Society will also be invited to assist with recruitment. Recruitment through these services will be undertaken using the same approach as that used with NHS services. In addition, researchers may attend carer education/support groups to discuss the study and identify any interested carers or may promote the study via their newsletters.

6.1.4 Monitoring recruitment

After 50 carers have been recruited to the study we will undertake summary statistics to assess the mix of carers in terms of dementia severity, gender, relationship and mix of deprivation.

6.2 Obtaining consent

Telephone or email contact with the research team will enable carers to be screened for eligibility and to provide more details about the study and answer carers' questions. The research team will maintain a log of calls for those who do not proceed to an interview. This log will not record any identifiable information but will record reasons why the person was not eligible or did not want to participate, along with the date of the call and where they had been informed about the study.

If the carer is eligible and interested in being involved they will be sent a copy of the PIS (Appendix 6). After 3 days we will telephone them to ask if they have read the PIS and are still happy to be involved. If they are, a time and date will be arranged for the quantitative interview. Interviews will be conducted in a location suitable for the carer – either in their own home, at a meeting room on the [name] or another location of their choice (provided it is suitable for a private, quiet conversation). Researchers will follow the UCL lone worker policy. Once a date has been agreed, carers will be sent a letter confirming the interview details (See Appendix 7) and asking they complete the enclosed Health Literacy Questionnaire (HLQ, Appendix 2). They will be able to complete the HLQ before the interview if they wish to reduce the number of questionnaires that will need to be undertaken on the day of the interview.

A sub-sample of carers (see selection criteria in Section 4.2) will be asked whether they would also like to take part in the additional qualitative semi-structured interview. We will endeavour to complete both the quantitative and qualitative interviews on the same day but will give carers the option of splitting it over two days if they want a break. The PIS indicates that only 20 carers will be invited for this additional component. Carers will be given this option at the end of the quantitative interview based on the purposive sampling strategy described in Section 4.2. They will either be able to continue on with the second interview or an alternative interview date will be arranged.

On the day of the quantitative interview, the researcher will go through the details on the PIS and check that the carer understands all parts of the PIS. The carer will be given an opportunity to ask any questions and be reminded that they can withdraw participation at any time. If they are still happy to participate they will be asked to complete and sign two copies of the consent form (Appendix 8) before commencing the interview(s). The researcher undertaking the interview will also sign both copies of the consent form. One copy along with the PIS will be left with the participant and the researcher will take the other copy of the consent form. The consent form also includes a question to consent to the research team contacting them within the next 2 years to be asked whether they are interested in participating in any extensions of this study or related research studies. In particular, the final work stream of the study will involve developing a resource for carers. Carers recruited for the interviews will be invited to support developing or testing this resource. Participation in this final work stream will involve signing a separate consent form with a study amendment or new ethics approval process.

6.3 Withdrawing from the study

During the consent process it will be explained to participants that they are free to withdraw at any stage. As the initial interview is conducted on the same day as consent is provided, it is unlikely that participants will want to withdraw from the study on the same day. If they find the interview difficult or long, however, they may wish to cease the interview. Data collected to this point will be included in the analysis (if sufficient to warrant inclusion) as long as the participant agrees.

6.4 What happens if a participant loses capacity after consenting?

As consent will take place on the same day as the interview it is unlikely that they could lose capacity within the same day. If they agree to take part in the second interview on a date in the future we will briefly review the Participant Information Sheet before completing the second interview to check that they still understand what participating involves and still have capacity to take part.

7 DATA ANALYSIS

7.1 Statistical Analysis

The statistical analysis will be overseen by the project statistician ([name]). Multivariable regression analysis will be used to enable us to explore the impact of a range of modifiable factors reflecting preparation for end of life on the MMCGI-SF, our main outcome. This type of analysis also allows us to control for potential confounding variables. The analysis will use the MMCGI-SF as the dependent variable with five predictor variables: knowledge of how dementia progresses; knowledge of the person with dementia's end of life preferences; having a lasting Power of Attorney or other formal advance directive in place; satisfaction with communication with healthcare providers; and satisfaction with support for health from your social network (detailed in Section 4.1).

The latter two items are extracted from the Health Literacy Questionnaire [28]. Health literacy is likely to be related to deprivation, which we will measure using the Townsend Deprivation Index. We will first examine whether there is collinearity between the health literacy and deprivation variables. If they are not related we will add deprivation as a covariate. Other potential confounding variables will be included in the analysis:

- Relationship type: being a spouse/partner, a child or another relationship (categorical variable; i.e. 2 covariates)
- Gender (binary measure)
- Care home status: living at home or in a care home (binary measure)
- Religiosity (continuous measure)

In total there are 10 potential covariates to be included in the model. A sample of 15 participants per covariate is preferable while ten may be sufficient.[34]. We will aim to recruit 150 participants for an adequately powered analysis.

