4.1 Quantitative interviews (n=150)

The study will aim to recruit 150 carers over a 15 month period starting in late 2017. The recruitment and consent process is described in detail in Section 6 and the power calculation in Section 7. Carers will provide written, informed consent before completing a face-to-face interview in a location of their choice. Previous experience in research with carers indicates that the majority will wish to be interviewed in their own home or the home of the person with dementia. Researchers will undertake the interview in pairs to begin with but on their own after training is complete. They will adhere to the UCL lone worker policy.

Researchers will ask questions and record answers on the Case Report Form (Appendix 1). The CRF contains demographic questions about the carer and some basic information about the person with dementia (such as dementia severity, type of diagnosis and time since diagnosis).

The Marwit-Meuser Caregiver Grief Inventory Short Form (MMCGI-SF) [25] will be used to assess severity of grief before death. This scale contains three subscales: heartfelt sadness and longing, worry and felt isolation, and personal sacrifice burden; a cutoff of 70/90 is considered a high level of grief.[25] The Clinical Dementia Rating scale will assess dementia severity based on the carer's report [26]. To test the primary hypothesis we will collect a number of measures to reflect the five modifiable factors that suggest preparation for end of life:

1. Greater knowledge of how dementia progresses (Dementia Knowledge Assessment Scale [27])
2. Greater knowledge of the person with dementia's end of life preferences (Discussed wishes regarding end of life with your relative? Have a good understanding of their wishes for end of life care?)
3. Having a lasting Power of Attorney or other formal advance directives in place - a proxy indication of "preparedness" (binary variable; any form of directive in place/not in place)
4. Higher satisfaction with communication with healthcare providers (Health Literacy Questionnaire [HLQ, excluding Social Support subscale] which examines how well carers understand health information and navigate the health system [28]) (See Appendix 2)
5. Higher satisfaction with support for health from social network (HLQ-Social Support subscale.[28])

A number of other measures have been included for other exploratory analysis and to control for possible confounders. These include:

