- Townsend Deprivation Index (identified through the participant's postcode)
- Hospital Anxiety and Depression Scale (HADS) [29]
- Relationship Closeness Scale [30] completed to reflect current relationship as well as relationship prior to dementia [31]
- Subscales (denial, self-blame, acceptance, active coping, humour, and substance abuse) from the Brief Coping Orientation to Problems Experienced scale (Brief COPE) [32]
- Religiosity using the Duke University Religion Index (DUREL) [33]
- Questions about the experience of taking part in the study (See justification and questions in Section 'Assessment and Management of Risk' in this protocol).

After agreeing to a date for the interview carers will be sent the Health Literacy Questionnaire (HLQ) [28] and be encouraged to complete this before the face-to-face interview. The purpose of this is to reduce the time required to complete the face-to-face interview so that it is less burdensome for the carer. The questionnaire is suitable for this purpose as it contains neutral questions about communicating with healthcare professionals.

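### Section 7.1 adjusts for Townsend deprivation only if it is unrelated to health literacy, so the rule as written omits it when it could confound the two HLQ predictors

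*Combined protocol and SAP*

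**What the plan says.** Section 7.1 sets out a multivariable regression of the MMCGI-SF grief score on five preparation predictors. Two of these, communication with healthcare providers and social support for health, come from the HLQ. On deprivation it makes three statements in sequence:

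- It expects an association: "Health literacy is likely to be related to deprivation, which we will measure using the Townsend Deprivation Index".
- It announces a preliminary collinearity check on those two sets of variables.
- It ends with the rule that depends on that check: "If they are not related we will add deprivation as a covariate".

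It gives no statistic or threshold for the check, and does not say what happens if the two are related. It then continues: "Other potential confounding variables will be included in the analysis". Relationship type, gender, care home status and religiosity follow, with no condition attached.

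On size it gives a total, "In total there are 10 potential covariates to be included in the model", and then the rule of thumb behind the target: "A sample of 15 participants per covariate is preferable while ten may be sufficient". The target is set at 150.

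Section 4.1 puts the Townsend index first in a list introduced by "A number of other measures have been included for other exploratory analysis and to control for possible confounders". No other section adjusts the grief model for deprivation or plans a comparison with and without it.

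**The concern.** The plan treats deprivation as a potential confounder: Section 4.1 collects it partly for that purpose, and Section 7.1 calls the covariates that follow the other ones. A variable can confound an HLQ coefficient only if it is associated with the HLQ score. For those two predictors, the literal rule therefore adds deprivation when it could not confound and omits it when it could. Omission is also the outcome the plan itself leads one to expect.

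If more deprived carers have lower HLQ scores and more grief, the HLQ coefficients absorb part of the deprivation effect, in the direction of the study hypothesis. The results are meant to guide a resource for carers, which could then target a factor that partly marks deprivation.

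Omission also leaves dementia knowledge, knowledge of end-of-life preferences and Power of Attorney unadjusted, although the check looks only at the HLQ. And because the check is undefined, two analysts could follow the same text and fit different primary models.

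**Working it through.** **1. The plan's own count.** Inputs are from Section 7.1, counting each predictor as one term.

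- Predictors 5 + relationship type 2 + gender 1 + care home status 1 + religiosity 1 = 10.
- 10 × 15 = 150, the stated target.

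Both figures reproduce, and only without Townsend. Reaching 10 with Townsend would require relationship type to count as one term, but the section counts it as two. With Townsend there are 11 terms: 150/11 = 13.6 participants per term, 11 × 15 = 165, and 11 × 10 = 110.

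**2. How weak a relation triggers omission.** If related means a correlation significant at two-sided 0.05 (assumed; the plan states no alpha), the smallest such |r| at N = 150 is t/√(148 + t²), with t the 97.5% point on 148 df. This gives 0.16.

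**3. Bias from omission.** The documents give none of these inputs, so all are assumptions, on standardised scales:

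- r, the size of the correlation of each HLQ score with deprivation (more deprived, lower score): 0.3 or 0.5.
- b, the deprivation effect on grief: 0.1, 0.2 or 0.3 SD.
- ρ, the correlation between the two HLQ scores: 0.5.
- True HLQ effects zero; the eight other terms independent of the HLQ and deprivation.

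Bias per HLQ coefficient = −b·r/(1 + ρ). With b = 0.3:

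- r = 0.3: 0.3 × 0.3/1.5 = 0.06 SD.
- r = 0.5: 0.3 × 0.5/1.5 = 0.10 SD.

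**4. False-positive rate.** With ten terms there are 150 − 11 = 139 residual df. The HLQ terms explain R² = 2b²r²/(1 + ρ), and SE = √[(1 − R²)/((1 − ρ²) × 139)]. With b = 0.3:

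- r = 0.3: R² = 0.0108, SE = 0.0974, bias/SE = 0.62. The noncentral t gives about 9% rejection.
- r = 0.5: R² = 0.030, SE = 0.0965, bias/SE = 1.04, giving about 18%.

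Simulation of the literal rule (omit if either HLQ score correlates with deprivation at p < 0.05; 6,000 studies per cell) agrees:

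| r | b (SD) | Bias per coefficient (SD) | Type I error per coefficient | At least one false HLQ finding |
|---|---|---|---|---|
| 0.3 | 0.1 / 0.2 / 0.3 | −0.02 / −0.04 / −0.06 | 5% / 7% / 9% | 10% / 13% / 18% |
| 0.5 | 0.1 / 0.2 / 0.3 | −0.03 / −0.07 / −0.10 | 6% / 10% / 18% | 12% / 20% / 35% |

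Deprivation is omitted in 99% of studies at r = 0.3. Always adjusting gives 5% per coefficient and 9% for at least one. With b = 0 the literal rule also gives 5%, so the harm is omitted-variable bias and not the preliminary test.

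**5. Sensitivity.**

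- HLQ inter-correlation 0.3 or 0.7, b = 0.3: type I error 12% or 7% at r = 0.3, and 26% or 12% at r = 0.5.
- Cut-off |r| > 0.3: deprivation dropped in 68% of studies at r = 0.3 and 100% at r = 0.5.
- Cut-off VIF > 2.5 or > 5: dropped in 0%, with no bias.

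**The case against.** The strongest reply is that the authors meant not collinear. The sentence just before the rule announces a collinearity check, and a rule designed to discard a measure collected partly for confounder control would be odd. On that reading, with a usual VIF cut-off, deprivation stays in and nothing is lost. This is plausible and cannot be excluded. But the operative words are not related, there is no threshold, and the plan's count of 10 matches a model without Townsend. Even strong collinearity would not justify dropping a confounder: keeping it costs precision, while dropping it costs bias.

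Second, the size is assumed throughout, and the simulation makes the other terms independent of deprivation, although Section 2 says socioeconomic factors influence preparation generally. This has force. Suppose the other three preparation predictors each correlate 0.3 with deprivation, with the HLQ scores and with one another (b = 0.3, ρ = 0.5). HLQ bias falls to about 0.034 SD at r = 0.3 and 0.085 SD at r = 0.5, and type I error to about 6% and 14%. The other three predictors then carry bias of their own, about 0.044 and 0.024 SD. The harm is spread rather than removed.

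Third, deprivation unrelated to the HLQ could still confound those three predictors, so adding it in that case is not useless. That is right: the rule is backwards for the HLQ predictors specifically.

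Fourth, the count of 10 is consistent with a conditional covariate, and 13.6 per term still exceeds the plan's minimum of 10. That also stands. The count is a consequential edit and not a separate error.

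**Conclusion.** The concern holds. As written, the rule omits a potential confounder of the plan's own choosing in the situation where it could confound the two HLQ predictors, and the plan expects that situation.

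The consequence ranges from negligible to moderate. Over the main grid, type I error per HLQ coefficient is 5% to 9% at r = 0.3 and 6% to 18% at r = 0.5, against 5% with adjustment. The upper figures need a 0.3 SD deprivation effect, and all inputs are assumed. There is no bias if deprivation does not affect grief, or if the authors apply a usual VIF cut-off. The wording should be corrected before analysis, but the point does not undermine the study design.

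**What to change.** Replace the conditional sentence in Section 7.1 with text such as:

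> Townsend deprivation will be included as a covariate in the primary model whatever its correlation with the HLQ scores. Variance inflation factors will be reported. A model without deprivation will be shown only as a sensitivity analysis.

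In the same section change the covariate total from 10 to 11 and state the ratio as 13.6 participants per covariate at N = 150. This is below the preferred 15 (which would need 165) and above the stated minimum of 10, so the target need not change. The total of 11 assumes one term per predictor. Section 4.1 gives two questions for end-of-life preferences; entered separately they would make 12 terms and 150/12 = 12.5 per term.

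The cost is two edits and one model term, with no new data, since Townsend is already collected. With both HLQ scores in the model (ρ = 0.5), and for a given residual variance, the variance of an HLQ coefficient is multiplied by (1 − ρ²)(1 − r²)/(1 − ρ² − 2r² + 2ρr²):

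- r = 0.3: 0.6825/0.66 = 1.034, so the standard error rises about 2%.
- r = 0.5: 0.5625/0.50 = 1.125, so the standard error rises about 6%.

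The VIF of Townsend is 1/(1 − 2r²/(1 + ρ)): 1/(1 − 0.12) = 1.14 at r = 0.3 and 1/(1 − 0.333) = 1.50 at r = 0.5.

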1 INTRODUCTION

The course of dementia over many years, gradual losses and uncertain life expectancy can mean that family carers experience feelings and symptoms of grief before the death of the person for whom they are caring. UK guidelines recommending that carers are offered information about bereavement supports and dementia progression are rarely followed in practice.

This study aims to examine the relationship between carers' feelings of grief before the death of a person with dementia and how well they are prepared for that death. The study involves completing a questionnaire schedule with 150 carers of people with dementia (across all stages of dementia and for people with dementia living at home or in a care home). Twenty of these carers will be purposively selected to complete an additional semi-structured interview to further explore the research questions. The questionnaires will examine whether being prepared for end of life is linked to having lower levels of grief. Preparation will be measured by important factors shown in research including: knowledge of dementia progression; knowledge of the person with dementia's end of life preferences; communication with healthcare professionals; family support; and having a Power of Attorney or advance directive in place. The study is one component of a larger senior fellowship being undertaken by the CI and will inform subsequent development of a resource for supporting carers to help prepare for end of life care and manage grief. The study was informed by the Alzheimer's Society Research Network who will also be involved throughout the study. It will increase understandings of how we can better support grieving carers and help them plan and prepare for end of life care. This is a critical area given that dementia is now the leading cause of death in the UK [1] and family and friend carers are relied on to meet an ever increasing proportion of the support and care needs for their relatives living with dementia in this time of austerity.

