2 BACKGROUND AND RATIONALE

Grief is often felt before the death of a friend or relative with dementia. Grief before the death can be triggered by losses associated with dementia causing carers to experience sorrow, anger, yearning and acceptance that can wax and wane from diagnosis to the end of life [2]. It occurs due to the lengthy and uncertain disease trajectory; compromised communication between the person with dementia and family and friends; and changes in relationship quality and carer freedom.[2] Grief before the death can contribute to carer burden and depression.[2] Between 47-71% of family carers of people with dementia experience grief before the death and 20% experience complicated grief after the death.[3] Higher grief prior to death is associated with complicated grief after death [4], so emotional support during care rather than solely after the death may be beneficial.[5]

Preparation for end of life has medical, psychosocial, spiritual and practical components, [6, 7] including having a family member or healthcare professional to help make decisions, knowing what to expect about the terminal condition and having finances in place.[8] Good communication with healthcare providers to discuss prognosis, treatments, cultural, spiritual and practical issues; and dealing with family conflict is critical.[6] Preparation for end of life is associated with a lower likelihood of complicated grief in bereavement [9-11] but has not been explored in the context of grief before the death (Figure 1). Preparation for end of life is influenced by socioeconomic factors associated with health literacy (Figure 1). Low health literacy is more common amongst those from more deprived backgrounds, ethnic minorities, older people and those with chronic health conditions.[12] In the UK a third of older adults have difficulty interpreting basic health information.[13] Despite the potential benefits of end of life discussions with carers, there are many barriers to such discussions.[14, 15] Carers struggle to formalise in writing future wishes on behalf of the person with dementia and professionals tend to be reluctant to initiate end of life discussions.[16] Family conflict can deter end of life decision making.[17] Factors reflecting preparation for end of life are potentially modifiable suggesting that improving preparation could reduce grief before the death.

[figure not shown]

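### The primary regression leaves out dementia severity, although the study measures it and samples every stage, so the preparation–grief coefficients are open to confounding by stage

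*Combined protocol and SAP*

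**What the plan says.** Section 7.1 regresses the grief score (MMCGI-SF) on five preparation factors: knowledge of dementia progression, knowledge of end of life wishes, a Power of Attorney or directive in place, and two predictors taken from the Health Literacy Questionnaire (HLQ). It then says "Other potential confounding variables will be included in the analysis" and lists relationship type (two terms), gender, care home status and religiosity. Deprivation is added only if it proves unrelated to health literacy. The stated total is 10, and the sample size rests on this rule: "A sample of 15 participants per covariate is preferable while ten may be sufficient".

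Dementia severity is not in that list, nor among the additional measures that Section 4.1 keeps for confounder control and exploratory work. No stratified, interaction or sensitivity analysis by severity is planned.

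Elsewhere the protocol treats stage as important:

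- Section 1 recruits carers "across all stages of dementia and for people with dementia living at home or in a care home".
- Section 4.1 measures it: "The Clinical Dementia Rating scale will assess dementia severity based on the carer's report". The case report form also holds "dementia severity, type of diagnosis and time since diagnosis".
- Section 2 says: "Grief before the death can be triggered by losses associated with dementia".
- Section 6.1.4 produces summary statistics after 50 carers to "assess the mix of carers in terms of dementia severity, gender, relationship and mix of deprivation".

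**The concern.** The hypothesis in Section 3.1 is that preparation goes with lower grief. Stage is a candidate common cause. As dementia advances, carers may learn more about progression, discuss wishes and put a directive in place, and their grief may change as losses accumulate. The link is most plausible for those three predictors. The documents give no reason to expect it for the two HLQ predictors.

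If stage is related to preparation and grief in the same direction, leaving it out pulls a protective coefficient towards zero. If it is related to them in opposite directions, the bias favours the hypothesis. From the planned model alone a reader could not tell which had happened, and a severity term added once results are known would be post hoc. The results are meant to guide a resource for carers (Section 2), so a masked or spurious association would carry forward.

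**Working it through.** **1. The plan's term count.** 5 predictors + 2 relationship + 1 gender + 1 care home + 1 religiosity = 10, and 10 × 15 = 150. This reproduces the target, but only without deprivation and without severity.

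**2. Size of the bias.** The documents give no severity–grief or severity–preparation association, so every input here is an assumption except N = 150 and the term count. All variables are standardised. The true coefficient is -0.20 for the predictor of interest and zero for the others. Care home share is 30%, with latent correlation 0.6 with severity. The severity–preparation correlation is 0.3 and the severity effect on grief is 0.3. Tests are two-sided at 5%.

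Shift = (coefficient of the predictor when severity is regressed on the terms in the model) × (effect of severity on grief).

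Worked for the case where one predictor tracks stage:

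- Correlation of care home status with severity: 0.6 × 0.3477 / √(0.3 × 0.7) = 0.455, where 0.3477 is the normal density at the 70th centile.
- Correlation of the predictor with care home status, through severity: 0.3 × 0.455 = 0.137.
- Coefficient in the severity regression: (0.3 − 0.137 × 0.455) / (1 − 0.137²) = 0.242.
- Shift: 0.242 × 0.3 = 0.073. Expected estimate: −0.20 + 0.073 = −0.127.
- Standard error without CDR (139 df): 0.084. Shift / SE = 0.86. Noncentral-t power is 32%.
- Standard error with CDR (138 df): 0.085. Power is 65%.

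The same calculation for four patterns:

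| Predictors tracking stage | Shift (SD) | Shift / SE | Estimate without CDR | Power without / with CDR | False-positive rate, true effect zero |
|---|---|---|---|---|---|
| One | 0.073 | 0.86 | −0.127 | 32% / 65% | 13.7% |
| Five, correlated only through stage | 0.056 | 0.67 | −0.144 | 39% / 65% | 10.1% |
| Three, intercorrelated 0.3 | 0.046 | 0.51 | −0.154 | 40% / 61% | 8.0% |
| Five, intercorrelated 0.3 | 0.034 | 0.37 | −0.166 | 43% / 59% | 6.5% |

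With the severity–grief sign reversed, the shift has the same size in the other direction and the estimate is −0.23 to −0.27. A simulation of 4,000 studies per scenario agreed: −0.128 without CDR and −0.201 with it in the one-predictor case, −0.164 and −0.199 in the last row.

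**3. Sensitivity to the assumptions.**

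- Associations of 0.2 each: shift 0.015 to 0.032 SD. The false-positive rate is 5.3% to 6.6% in the one-predictor and both five-predictor cases.
- Associations of 0.1 each: shift under 0.01 SD. If either association is zero, the shift is zero.
- Care home correlation with severity of 0.8 instead of 0.6: the top shift falls from 0.073 to 0.059 and the bottom from 0.034 to 0.028.
- Care home share of 20% to 50%: the shift changes by at most 0.002.
- Three predictors tracking stage, with all five intercorrelated 0.3: shift 0.063.

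**4. Price of adding CDR if it does not matter.** With no severity effect on grief, one CDR term raises the standard error by about 1% to 4% and costs about 1 to 4 points of power.

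**The case against.** The strongest reply is that nothing in the documents shows confounding. Section 2 describes grief as rising and falling over the illness, not as a gradient with stage, and no section says that preparation changes with stage. Choosing 0.3 for both associations makes the problem look larger than 0.2 would. This stands as a limit on size: the bias could be negligible. It does not remove the exposure, because the protocol's own rationale links grief to the losses of dementia and the design makes stage vary.

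Care home status is in the model and carries some information on stage. That is true, and the calculation keeps it in. But one binary variable cannot separate stages among people living at home, and even a 0.8 correlation leaves most of the shift.

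Section 6.1.4 concerns recruitment mix and is not a confounder list. That is fair. It shows only that the investigators thought severity worth watching alongside gender, relationship and deprivation, all of which reach the model (deprivation conditionally).

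The five-predictor rows go beyond what the documents support for the HLQ predictors. This also stands, but those rows do not set the top of the range.

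Finally, CDR comes from the carer's report, so dementia knowledge or grief itself may colour the rating, and a single interview does not fix the order of events. Adjustment is therefore not free of bias either. That is a reason to report both models, not to leave severity out. Because CDR is collected, a comparison could still be made later; what would be lost is pre-specification.

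**Conclusion.** The concern holds. As written, the primary model omits a measured variable that the protocol's own reasoning makes a plausible confounder, and no reason is given. The size and direction of the bias cannot be known from the documents. With assumed associations of 0.3 each, it is 0.4 to 0.9 of a standard error, enough to cut power from about 60% to between 32% and 43%, or to raise the false-positive rate to between 6.5% and 13.7%. With weaker associations it is small or nil. The figures with CDR included assume a linear severity effect fully captured by the rating. The point should be fixed before analysis, but it does not invalidate the design.

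**What to change.** In Section 7.1, pre-specify CDR as a term in the primary model and state its coding: one score term, or a few categories if the relation is not taken to be linear. Report the model without CDR as a planned sensitivity analysis; this also covers the possibility that carer-reported severity is coloured by knowledge or grief. A further sensitivity model with time since diagnosis, already collected, is optional.

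Restate the term count and the sample-size justification:

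- One CDR term: 11 terms, or 12 with deprivation. 150/11 = 13.6 and 150/12 = 12.5 participants per term.
- Three category terms: 13 or 14 terms. 150/13 = 11.5 and 150/14 = 10.7.
- Four category terms plus deprivation: 15 terms. 150/15 = 10.0, exactly the plan's minimum.

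The preferred 15 per term is lost, but the minimum of ten is met in every case. The change is to analysis-plan wording only: no new data, at least one degree of freedom, and the small loss of precision shown above if severity turns out not to matter.
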